4.6.3 Deaths

Numbers and frequencies of deaths during double-blind period occurring until 28 days after the last dose of double-blind treatment will be presented by treatment arm. Deaths occurring more than 28 days after last dose for patients who did not enter the safety-follow-up period will also be presented separately.

Pirfenidone — F. Hoffmann-La Roche Ltd

All information associated with deaths collected in eCRF panel on study discontinuation will be listed. A flag variable will be included in the listing specifying the study period when the death occurred.

4.6.4 Laboratory Data

All of the laboratory tests will be conducted by the trial site's local laboratory.

All parameters will be graded according to NCI CTCAE (CTEP 2010), version 4.03, if applicable. Laboratory parameters that cannot be graded according to the corresponding NCI CTCAE version 4.03 will be assessed with respect to normal range (low, normal, high).

Laboratory parameters including hematology and the chemistry panel will be presented in shift tables of NCI-CTCAE version 4.03 grade at baseline versus worst grade during randomized double-blind treatment period. The laboratory parameters will be presented according to means, standard deviation, minimum, and maximum. Selected laboratory parameters will be also graphically presented over time.

The following laboratory samples will be collected:

- Hematology: white blood cell (WBC) count, red blood cell (RBC) count, hemoglobin, hematocrit, platelet count, differential count (neutrophils, eosinophils, basophils, monocytes, lymphocytes, other cells).
- Chemistry panel (serum or plasma): sodium, potassium, chloride, bicarbonate, glucose, blood urea nitrogen (BUN) or urea, creatinine, total protein, albumin, phosphorus, calcium, total and direct bilirubin, alkaline phosphatase, ALT, AST, uric acid, lactate dehydrogenase (LDH).

Clinical laboratory values will be presented separately for CTCAE-gradable and non-CTCAE gradable parameters by laboratory panel (hematology, serum chemistry). For laboratory analyses, visits will be assigned to visit windows as described in Section 4.10. This will also be valid for possible unscheduled visits. In case that multiple evaluable assessments occur within the same visit, the nearest to midpoints value will be used for analyses.

The following summaries will be prepared:

For each laboratory parameter, descriptive statistics of laboratory values at each scheduled visit (derived as described above), and absolute changes from baseline to post-baseline will be presented by treatment arm.

Shift tables presenting categorical changes in CTCAE grade from baseline to worst grade recorded during the double-blind period, in the indicated direction, will be provided for CTCAE-gradable parameters by treatment arm. If no CTCAE grade is available for a specific laboratory variable, shift tables will present worst changes with respect to normal range category (low, normal, high).

Pirfenidone — F. Hoffmann-La Roche Ltd

Liver abnormalities (total bilirubin, alkaline phosphatase, ALAT (SGPT), ASAT (SGOT)) of Grade 3 and 4 will be presented showing numbers and percentages of patients for each parameter separately. Line graphs of liver parameters will be provided.

4.6.5 Vital Signs

Vital signs will include measurements of respiratory rate (breaths/min), pulse rate (beats/min), and systolic and diastolic blood pressures (mmHg) while the patient is in a seated position, temperature (C) and weight (kg). Vital signs will be assigned to visit windows as per Section 4.10. Descriptive statistics will be used to summarize vital signs data at baseline and at each scheduled post-baseline visit, and for the absolute change from baseline to each scheduled post-baseline visit by treatment arm during double-blind period.

4.6.6 ECG

Single ECG recordings will be obtained at specified time points, as outlined in the Schedule of Assessments (see Appendix 2), and may be obtained at unscheduled time points as indicated.

The following should be recorded in the appropriate eCRF: heart rate (beats/min), RR interval (msec), QRS interval (msec), PR duration (msec), uncorrected QT interval (msec), and the QTcF based on the machine readings of the individual ECG tracings. Any morphologic waveform changes or other ECG abnormalities must be documented on the eCRF. If considered appropriate by the Sponsor, ECGs may be analyzed retrospectively at a central laboratory.

QTcF values of the safety population will be assigned to the following intervals: < 500 ms, 500–550 ms, and > 550 ms. Numbers and percentages of patients with their maximum QTcF interval category will be summarized by treatment arm over time. Absolute changes from the Baseline to each post-baseline visit in QTcF values will be categorized to < 31 ms, 31–60 ms, and > 60 ms. Numbers and percentages of patients in each category will be presented by treatment arm for each post-baseline visit or treatment discontinuation. Planned visits will be used for presentations.

Descriptive statistics for heart rate, RR interval, QRS interval, PR duration, uncorrected QT interval, and the QTcF will be presented for each visit by treatment arm.

A listing containing ECG data will be presented.

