4.5.9 Electrocardiograms

Single ECG recordings will be obtained at specified time points, as outlined in the Schedule of Assessments (see [Appendix 1](#)), and may be obtained at unscheduled time points as indicated.

All ECG recordings must be performed using a standard high-quality, high-fidelity digital electrocardiograph machine equipped with computer-based interval measurements. Lead placement should be as consistent as possible. ECG recordings must be performed after the patient has been resting in a supine position for at least 10 minutes. All ECGs, when possible, should be obtained prior to other procedures scheduled at the same time (e.g., vital sign measurements, blood draws). Circumstances that may induce changes in heart rate, including environmental distractions (e.g., television, radio, conversation) should be avoided during the pre-ECG resting period and during ECG recording.

For safety monitoring purposes, the investigator must review, sign, and date all ECG tracings. Paper copies of ECG tracings will be kept as part of the patient's permanent trial file at the site. Digital recordings will be stored at site. The following should be recorded in the appropriate eCRF: heart rate, RR interval, QRS interval, PR duration, uncorrected QT interval, and the QTcF based on the machine readings of the individual ECG tracings. Any morphologic waveform changes or other ECG abnormalities must be documented on the eCRF. If considered appropriate by the Sponsor, ECGs may be analyzed retrospectively at a central laboratory. Refer to section 5.1.1.8 for details on protocol management of increases in QT interval.

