5.1.1.8 Management of Increases in QT Interval

In the event of a QTcF interval of >500 ms or an increase from baseline of >60 ms, a repeat ECG must be obtained within 24 hours. If the QTcF finding is confirmed by the repeat ECG and verified by the site (trial center) or local cardiologist, pirfenidone treatment should be discontinued and a decision on trial treatment discontinuation should be made, as described in Section 4.6.1.. If an alternative explanation is identified (e.g., electrolyte abnormalities, co-medications known to prolong the QT interval, and

severe bradycardia) and the abnormality resolves, restarting trial treatment should be considered by the investigator in consultation with the Medical Monitor or designee. If the investigator, in consultation with the Medical Monitor or designee, considers it clinically appropriate to recommence trial treatment, treatment should be restarted as described in [Table 2](#) .

5.1.2 **Management of Patients Who Experience Specific Adverse Events**

Guidelines for management of specific adverse events are outlined in [Table 3](#) .

Table 3 Guidelines for Management of Patients Who Experience Specific Adverse Events with Pirfenidone

Event	Action to Be Taken
Elevated aminotransferase results	
 • For patients with a >3 to <5 × ULN increase in ALT or AST levels without hyperbilirubinemia: 
 • Discontinue confounding medications • Monitor the patient closely, including repeating liver chemistry tests • Maintain the full daily dose, if clinically appropriate, or reduce or interrupt the dose (e.g., until liver chemistry test results are within normal limits) with subsequent re-titration to full dose if well tolerated. • For patients with a >3 to <5 × ULN increase in ALT or AST levels with symptoms or hyperbilirubinemia: 
 • Discontinue pirfenidone and do not rechallenge the patient. • For patients with a >5 × ULN increase in ALT or AST levels: 
 • Trial treatment should be permanently discontinued.
Gastrointestinal disorders	
 • Dose modifications may be necessary in some cases of gastrointestinal adverse reactions. • Taking pirfenidone with food is recommended.

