Cases of potential drug-induced liver injury that include an elevated ALT or AST in combination with either an elevated bilirubin or clinical jaundice, as defined by Hy's law: [ALT or AST >3 x ULN + total bilirubin >2 x ULN]

- Any and any related hepatic side effects: elevations in ALT and AST >3 × ULN at the same timepoint in the study.
- Any and any related gastrointestinal (GI) disorder (MedDRA SOC: GI Disorders)
- Any and any related photosensitivity (MedDRA Preferred terms Nodular rash, Photodermatosis, Photosensitivity reaction, Pruritus, Pruritus generalized). Potential updates in those terms will be needed in case the MedDRA version changes.
- Any and any related rash (MedDRA Preferred terms Rash, Rash erythematous, Rash generalized, Rash macular, Rash maculo-papular, Rash papular, Rash pruritic, Solar dermatitis, Solar urticarial, , Sunburn, Erythema, Dry skin). Potential updates in those terms will be needed in case the MedDRA version changes.
- Angioedema (MedDRA preferred term Angioedema).
- Dizziness (MedDRA preferred term Dizziness).
- Fatigue (MedDRA preferred term Fatigue).
- Weight loss (MedDRA preferred term Weight loss).
- Increase in QT interval: In the event of a QTcF interval of >500 ms or an increase from baseline of >60 ms, a repeat ECG must be obtained within 24 hours.
- Any and any related TEAE leading to death
- Any and any related TEAE leading to treatment discontinuation

Pirfenidone — F. Hoffmann-La Roche Ltd

- Any grade 3-4 laboratory liver test results
 - o ASAT (SGOT) results
 - o ALAT (SGPT) results
 - o alkaline phosphatase results
 - o total bilirubin results

The incidence of TEAEs, related TEAEs, non-serious TEAEs, serious TEAEs, related serious TEAEs, grade 3-5 TEAEs and TEAEs leading to treatment discontinuation, dose modification or death will be summarized by treatment arm, by system organ class (SOC) and preferred term (PT) on the basis of the safety population. Frequencies and percentages of patients experiencing (at least) one event in the respective category will be presented by decreasing frequencies. If patients have more than one AE within a SOC or PT they will be counted only once for the respective SOC or PT. Additionally the total numbers of TEAEs will be provided for each SOC and overall.

Similar summary presentations will be provided for the incidence of TEAEs leading to dose reduction and drug interruption and TEAEs leading to hospitalization.

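### The maximum-QTcF table in SAP 4.6.6 is confined to planned visits, so peaks on unscheduled or higher repeat ECGs are left out and the maximum can be understated

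*SAP*

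**What the plan says.** SAP 4.6.6 (version 3.0) describes two categorical QTcF displays.

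- Absolute values: "QTcF values of the safety population will be assigned to the following intervals: < 500 ms, 500–550 ms, and > 550 ms". For these, "Numbers and percentages of patients with their maximum QTcF interval category will be summarized by treatment arm over time".
- Change from baseline at each post-baseline visit: values "will be categorized to < 31 ms, 31–60 ms, and > 60 ms".

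The paragraph closes with "Planned visits will be used for presentations". The section also plans descriptive statistics by visit and a listing of ECG data.

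Protocol 4.5.9 says that ECGs "may be obtained at unscheduled time points as indicated", and SAP 4.6.6 repeats this. Protocol 5.1.1.8 sets the QT rule, with a 24-hour limit for the repeat: "In the event of a QTcF interval of >500 ms or an increase from baseline of >60 ms, a repeat ECG must be obtained". Action on trial treatment then depends on the repeat and on verification at the site or by a cardiologist.

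The safety overview in SAP 4.6.2, which counts patients by arm, has a row that reads: "Increase in QT interval: In the event of a QTcF interval of >500 ms or an increase from baseline of >60 ms, a repeat ECG" and continues with the rest of the management instruction.

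**The concern.** A per-patient maximum is meant to capture the worst value observed. Restricting it to planned visits removes the tracings most likely to hold that value: those taken because of symptoms or a new co-medication, and the repeats that the protocol itself requires. The SAP treats laboratory data differently. Section 4.6.4 brings unscheduled laboratory values into the visit windows and tabulates the worst grade over the double-blind period. Section 4.9 applies visit windows to vital signs and laboratory data and does not name ECGs.

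Twelve-lead ECGs are a named safety endpoint (protocol Section 2, SAP 2.2.4). The maximum-category table is the display in 4.6.6 that would show an imbalance in extreme values between arms. The other display that could do so, the QT row in 4.6.2, does not say which ECGs feed it.

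**Working it through.** The plan states no figure to reproduce here. The check is of which ECGs can reach the tables, and of how the categories compare with the protocol rule.

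**1. Planned post-baseline ECGs** (protocol Appendix 1 and its footnotes; visit window ±5 days)

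| Visit | Planned day | Permitted days |
|---|---|---|
| Week 12 | 84 | 79 to 89 |
| Week 24 | 168 | 163 to 173 |
| Early discontinuation | last dose + 28 | last dose + 23 to + 33 |
| Week 28 | 196 | 191 to 201 |

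Week 28 falls 196 − 168 = 28 days after the end of double-blind treatment. Only the first two visits can be on drug.

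**2. Direction of the error.** Let P be a patient's planned post-baseline ECGs and U the unscheduled and repeat ones. The table uses max(P), whereas the worst observed value is max(P ∪ U). Since max(P) ≤ max(P ∪ U), the table can be right or too low, never too high. It is too low when the highest value lies in U. A repeat prompted by a planned ECG does not remove that planned value; only a repeat higher than it is lost.

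**3. On-drug planned ECGs by day of last dose, L** (visits attended within window)

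- L before Day 79: none.
- L from Day 79 to 88: none or one, depending on the date of the Week 12 visit.
- L from Day 89 to 162: one.
- L from Day 163: one or two, depending on the date of the Week 24 visit.

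**4. Post-drug ECGs and the safety window.** SAP 4.2.4 counts safety assessments as on-treatment up to 28 days beyond the last positive dose. The discontinuation visit may fall on any of 33 − 23 + 1 = 11 days. Of these, days 29 to 33 (5 of 11) lie outside the window. A patient who stops before the Week 12 ECG therefore has only an off-drug planned tracing after baseline, and that tracing may or may not count as on-treatment.

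**5. Cut-offs.** The two upper absolute bands together mean QTcF ≥ 500 ms, against > 500 ms in protocol 5.1.1.8. Comparing every whole-millisecond value from 350 to 700 gives one disagreement, at exactly 500 ms. The > 60 ms change band agrees with the protocol at every value checked.

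**6. The either/or criterion.** Section 4.6.6 has no single count of patients above 500 ms or above 60 ms. The criterion does appear in the 4.6.2 overview row, but joined to an instruction to repeat the ECG. That row does not say whether planned, unscheduled or repeat tracings are used.

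**The case against.** The strongest reply is that the planned-visit sentence closes a paragraph about by-visit categories and may mean only that nominal visit labels are used instead of derived windows. It does not expressly exclude unscheduled values from a patient's maximum. That reading is possible, but it does not rescue the table. An unscheduled tracing carries no planned-visit label and ECGs have no windowing rule, so it still has no route in.

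Other parts of the reply stand, and they limit what a reader may infer.

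- **That such values vanish from the report.** They do not. They should be in the ECG listing. An ECG deterioration with symptoms, or one that leads to a change of trial or concomitant treatment, is an adverse event under protocol 5.2.1 and enters the tables of SAP 4.6.2. Neither route gives a worst-case count of measured values by arm.
- **That the cut-offs cause peaks to be lost.** They lose none; the difference is confined to exactly 500 ms.
- **That the protocol's either/or rule is nowhere counted.** The 4.6.2 row contains it. What is missing is a definition that can be programmed.
- **That all early stoppers contribute only off-drug ECGs.** This holds only for those who stop before their Week 12 ECG, and it follows from the visit schedule, not from the planned-visit sentence.

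On importance, the trial is described as hypothesis-generating, safety parameters are not formally tested (SAP 4.6), and QT prolongation is not among the adverse events of special interest in protocol 5.2.3. These facts keep the point modest, but they do not justify a maximum that omits available data.

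**Conclusion.** The concern holds in limited form. Followed as written, SAP 4.6.6 produces a maximum-QTcF table that leaves out peaks found only on unscheduled ECGs and repeat values higher than the planned one. The bias in the maximum can go only downward. The planned data are sparse: at most two on-drug post-baseline ECGs over 24 weeks, and none for anyone whose last dose precedes the Week 12 tracing.

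The conclusion assumes that visits fall in their permitted windows and that the planned-visit sentence governs the maximum table as well as the by-visit one. How many patients are affected, and whether the arms differ, cannot be computed from the documents. The point should be corrected because it concerns a named safety endpoint and costs little. It is not evidence that a QT signal has been missed.

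**What to change.** In SAP 4.6.6:

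- Derive each patient's worst-case QTcF and worst-case change from baseline from all post-baseline ECGs (planned, unscheduled and repeat) within the SAP's own on-treatment safety window, from first dose to 28 days beyond the last positive dose. Flag each ECG as taken on drug or after the last dose.
- Add counts by arm of patients with QTcF > 500 ms, with a rise > 60 ms, and with either.
- Keep planned visits for the by-visit summary statistics only.
- Reconcile the 500–550 ms band with the > 500 ms wording of protocol 5.1.1.8.

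In SAP 4.6.2, replace the copied repeat-ECG instruction in the QT row with the either count just defined.

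A split by whether the repeat ECG reproduced the finding is optional. Verification by the site or a cardiologist is not among the ECG items that protocol 4.5.9 lists for the eCRF, so a split on verified findings might need more than programming.

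The cost is SAP wording and table programming. Protocol 4.5.9 already requires QTcF from individual tracings on the eCRF. SAP 4.5.8 records that the primary analysis was run in March 2019, so the ECG tables would be rerun on existing data. The change does not supply on-drug ECGs for patients who stopped before Week 12; the flag only makes their absence visible.

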4.7 SAFETY FOLLOW-UP ANALYSES

Data collected during the safety- follow-up period will be analyzed in the following way.

Adverse events during the 12-month safety follow-up period for pirfenidone treatment will be defined as:

 AEs that started or worsened on or after the date of safety follow-up period start until the end of the safety follow-up.

Pirfenidone — F. Hoffmann-La Roche Ltd

The safety follow-up population will be used for these analyses.

Summary tables for the incidence of AEs, related AEs, serious AEs, related serious AEs, severe AEs and severe related AEs will be summarized by system organ class (SOC) and preferred term (PT). Frequencies and percentages of patients experiencing (at least) one event in the respective category will be presented by decreasing frequencies. If patients have more than one AE within a SOC or PT they will be counted only once for the respective SOC or PT. Additionally, the total numbers of AEs will be provided for each SOC and overall. As with the end of the double-blind treatment period, an overview of safety will also be presented.

Pirfenidone exposure during safety-follow-up will be analyzed in a similar fashion as described in Section 4.7.1 with regard to treatment duration and amount of drug intake.

Data of laboratory assessments (AST, ALT, bilirubin, and alkaline phosphatase) and vital signs during safety-follow-up period will be analyzed in a similar fashion as described in Section 4.7.4 and Section 4.7.5.

Data will be presented by randomized treatment labeled as 'Randomized Pirfenidone' and 'Randomized Placebo'.

4.8 MISSING DATA

With exception of the tipping point analysis described in section 4.5.8, missing data will not be imputed. Other exceptions will be made for the data related to adverse events and concomitant medications as described below.

For adverse events, missing start dates will only be imputed for determination of whether the adverse event is considered to be treatment-emergent or not.

Incomplete or missing onset dates will be imputed to the earliest date possible (using any reliable portions of the onset date that are available). The onset day is considered unreliable if the month or year portions of the date are missing.

In case the month portion of the AE start date is missing, the AE start date will be imputed to the earliest day possible by using the following principles:

- If Treatment Start Date is missing, then the AE Start Date will be imputed as 01-01-YYYY or the earliest date regarding signature of informed consent, screening date or randomization date, whichever is the later one
- When the Treatment Start Date is not missing, and the years of AE Start Date and Treatment Start Date coincide, the AE onset date will be set to the Treatment Start Date
- When the Treatment Start Date is not missing, and the years of the AE Start
 Date and the Treatment Start Date do not coincide, then the AE Start Date will be
 imputed as 01-01-YYYY or the earliest date regarding signature of informed
 consent, screening date or randomization date, whichever is the later one

Pirfenidone — F. Hoffmann-La Roche Ltd

In case the day portion of the AE Start Date is missing, the AE Start Date will be imputed to the earliest day possible as follows:

- If the Treatment Start Date is missing, then the AE Start Date will be imputed as 01-MMM-YYYY or the earliest date regarding signature of informed consent, screening date or randomization date, whichever is the later one
- When the treatment date is not missing, and the years and months from the AE Start Date and the Treatment Start Date coincide, the AE onset date will be set to the Treatment Start Date
- When the Treatment Start Date is not missing, and AE Start Date is after the Treatment Start Date according to the given year or month, then the AE Start Date will be imputed as 01-MMM-YYYY

If the AE stop date is missing, then the event will be assumed to be ongoing and a stop date will not be imputed.

In the case the treatment end date is missing and it cannot be judged whether the event occurred during the period of Treatment Start Date to Treatment End Date plus 28 days, the AE will be considered treatment-emergent as long as it is not flagged as prior AE.

For imputation and handling of missing intensity or relationship to study medication, please see Section 4.7.2.

All other missing or incomplete adverse event data will be left as missing.

For concomitant medications, missing start or end dates will only be imputed to determine whether the medication is considered to be prior, on-treatment, post-treatment.

In general if only the day is missing from the start date then the missing day will be imputed as 01-MMM-YYYY unless the month is the same month as the start of study medication in which case the missing date will be imputed as the treatment start date.

If both the day and month are missing from the start date then the start date will be imputed as 01-JAN-YYYY.

If both the day and month are missing from the start date year is the same as treatment start date then the start date will be imputed as 'treatment start date', but if the year is after treatment start date, the start date will be imputed as 01-JAN-YYYY.

If the day, month and year are all missing from the start date then the start date will be imputed as 01-JAN for the year in which the patient was recruited to the study.

If the day, month and year are all missing from the start date then the start date will be imputed as 'treatment start date'.

Pirfenidone — F. Hoffmann-La Roche Ltd

If an incomplete stop date has both the year and month present, the day will be imputed as the last day of the month or date of discontinuation/death.

If the AE is ongoing at time of primary analysis, concomitant medication will be summarized for the double-blind treatment period and safety follow-up.

